8.2 ANALYSES TWO: EFFECTS IN DIFFERENT POPULATION SUBGROUPS

The above analyses will be repeated in specific population groups, assuming appropriate numbers, based on demographic variables and other variables identified as important in analyses one.

8.3 ANALYSES THREE: BARRIERS AND FACILITATORS TOWARD DIETARY CHANGE

Qualitative data will be transcribed and analysed using thematic analysis following Braun and Clarkes 6-stage methodology (Braun and Clarke, 2006). These analyses will be aided by the use of NVIVO software, and reported using the Consolidated Criteria for Reporting Qualitative Research (COREQ) (Tong et al., 2007). Themes will be gained from the population as a whole, at different time points, and interpreted in combination with the data on free sugar intakes and adherence. Comparisons will be made between those who are successful and not successful at changing their free sugar intakes, and those who are adherent and not adherent to the recommendations.

9 DISCUSSION

Population estimates suggest that the majority of individuals do not achieve multiple nutrient or food-based dietary goals (Leme et al., 2021; Yau et al., 2019). Despite national public health programmes, individuals continue to overconsume nutrients, such as free sugars (Public Health England, 2020) with the health and budgetary benefits from dietary change (Public Health England, 2015) unlikely to come to fruition. This study seeks to extend the limited literature on the effectiveness of nutrient-, food-, and food-substitution-based recommendations using current PHE free sugar reducing advice. It will offer a new perspective on the efficacy of different dietary recommendations to enact behaviour change. The research has international relevance given widespread links between diet and disease (Roth et al., 2020) and low adherence to national dietary guidelines (Leme et al., 2021; Yau et al., 2019).

Declaration of interests: This trial is part of a PhD studentship, funded by Bournemouth University, UK, and The International Sweetener Association, BE.

Ethical approval: Ethics approval was gained from the Research Ethics Committee of Bournemouth University (Ethics ID: 30612). The standard protocol item recommendations for intervention trials (SPIRIT) guidelines (Chan et al., 2013) were used in the writing of this protocol and production of study documents.

Contributors: KA conceived the trial idea; LB and KA designed the trial with input from EAC and JJ. LB wrote the first draft of the trial protocol. All authors critically reviewed and revised the final version.

Funding: This trial will be funded by Bournemouth University, UK, and the International Sweetener Association (ISA), BE. The funders have offered limited comment on the trial design and materials but have had no role in the finalisation of the trial and will take no part in running the trial or interpreting the trial findings. The funders have had and will have no direct contact with the PhD student.

All food and drink items logged were checked individually using a variety of filters to analyse if the product was likely to contain free sugars. Filters included, 'text search' (broccoli), 'food name', 'food category', 'energy', 'kcal', 'carbohydrate' and 'sugar content'. Often multiple filters were used to increase the efficiency of recording, eg: search 'broccoli' and filter for lowest energy in kcal. First, it was decided which foods needed to be recorded, for example 'Sainsburys frozen broccoli' was unlikely to contain free sugars and therefore the original food code was kept with a 0 put into the free sugars column. For foods that did contain free sugars such as 'Cadbury mini eggs' these were recoded to another substitute food that had the full information on free sugars. The substitute coded item was selected by comparing the average of that food/drink item, and the comparative

nutritional values of energy (kcal), carbohydrates and sugars. For specific foods and brands, where it was unknown if the item was likely to contain free sugars, the ingredient list was researched online, using online grocery stores such as Ocado, Sainsburys, Tesco's, Asda and occasionally the brands own website. Every effort was put into retaining as many of the original food items as previously logged.

Once all items without free sugar data had been analysed to see if recoding was needed another spreadsheet was created, and these data were input into a separate sheet within CSV2. All 67406 individual food items were updated to a 100g value using the same method as previously mentioned. Then the 'XLOOKUP' function was utilised to identify which codes needed to be replaced and those that remained the same. The 'delta' function in a helper column was then used to compare the two columns of 'New' and 'Old' food code. All original items to be kept were then filtered and hidden in the spreadsheet. Only items which required recoding were now showing in the spreadsheet. The 'XLOOKUP' function was again used to match codes and replace all food names and nutritional values for recoded foods. Once completed, the spreadsheet was copied and pasted to remove all formulas and just retain the values. All substituted and non-substituted food items were then updated to their original quantities. The CSV2 file was then saved for backup.

This updated data from CSV2 was copied into a new file named CSV4. In CSV4 a helper column combining the participants ID number and log day (eg: JS19900.1, combination of JS1990 and 0.1) was used in combination with a new sheet to summarise all nutrients for each participant and each diet diary day. This resulted in 5120 unique daily totals across all nutrients. The CSV4 file was then saved as complete. Including all participants and screened non-participants a total of 70747 individual diary entries on the study via Nutritics Libro. Of these data, 67546 were participant entries and 3201 from non-participant screening diaries, with a total of 10757 unique food items logged.

Sweetener and sweet food counts

Foods that contained sweeteners, were high, medium or low in sugar were separated into counts for each diet diary. These counts were then added into 5 separate scores for the summation of foods consumed in each category for baseline, timepoints 1-4 and endpoint.

ALL DATA - MULTIPLE IMPUTATION

Main analyses were completed on an intention to treat basis as the gold standard for representing the applicability of the intervention in a real world setting rather than an ideal outcome. A variety of techniques to replace/analyse RCT results with missing data have been previously utilised including complete case analysis (CCA), single imputation (SI)(by last observation carried forward, mean or regression), multiple imputation or mixed-effect models (Bell et al., 2014; Li & Stuart, 2019; Ren et al., 2022). CCA and SI methods were discounted due to CCA not being reflective of real-world data, reducing statistical power and SI lacking uncertainty and most likely underestimating variance.

Instructions for the steps used to complete MI and the imputation sequence are included below. As multiple imputation is completed in the order of the variables within the analysis, the variables list was set as randomisation variables first, then nutrient values, anthropometrics and finally questionnaire data in the order that they were completed. All baseline variables were used as predictors, all endpoint variables used as imputations only due to the monotonic pattern.

Current literature suggests the optimal number of imputations varies between 5-20, with limited benefit over 5. Additional literature supports the number of imputations matching the percentage of attrition. Therefore, the number of imputations for the main analyses was set at 20 representing both the upper recommendation and percentage attrition.

Updates to SPSS now allow random selection of the closest of over >1 donor. Existing methodology and the amount of imputations suggest imputations via Predictive Mean Modelling are selected from the 5 closest donors making this more statistically robust than previous methods.

Before completing multiple imputation, the pattern of missing data was checked. Endpoint data presented as missing in a monotonic pattern. When imputing missing data values in SPSS the custom 'fully conditional specification (FCS)' in methods was selected over monotone. This was because FCS is suitable for both monotone and non-monotone patterned data and introduces Bayesian stochastic regression imputation as part of the predictive means multiple imputation methods. The benefit of this method results in imputed data being taken from both a donor and then adjusted to introduce a level of variability rather than just a copied result. Maximum iterations were set as 50 with FCS convergence checked post imputation. For all applicable statistical tests, analyses were run on each imputed dataset, with values pooled post analysis. This is because a pooled dataset prior to analysis does not just represent the average but retains the variability of the individual imputed datasets.

Where SPSS did not automatically pool results, Rubin's Rules for combining single estimates were used. The same multiple imputation guidelines were used for the basis for the imputation of all missing data. Where variables presented as having missing data, they were set as 'impute only' to ensure all predictor variables were not based on imputed data. The only difference was in one baseline waist circumference value that was missing in the original data and used in the 2nd MI predictors of the subsequent variables. This study took the premise of not generating imputations based on imputed data values. The same multiple imputation model was run for the initial analyses, adherence and variables completed by only lab participants. Multiple imputation for the adherence data used the same methods and predictors as for the main data set. The step by step methods used are included below. Adherence data points of each free sugar intake at each dietary data point were not included as predictors due to the fact that at least 1 time point needed to be imputed at each variable time point.

Instructions for multiple imputation in SPSS

1. Go to transform – random number generator. Select and set the active generator initialization at a fixed value of 950.
 - a. (This step is to provide a starting point/seed for the MI to enable results to be reproduced)
2. Then Analyze – multiple imputation – impute missing data values.
 - a. Variables tab
 - i. Input all variables for the model in the order they are to be used (this can be found in the output document and also to summarise at the end of this doc) but is all endpoint and corresponding baseline variables, therefore excluding demographics. But including gender. (The order is central for reproducing)
 - ii. Create a new data set – name ComA1_Impu
 - iii. Change imputations to 20
 - b. Method tab
 - i. Custom – select fully conditional specification (set to 50 iterations)
 - ii. Model type – change to PMM – chose from 5 closest (as is default)
 - c. Constraints tab
 - i. Scan data
 - ii. Under define constraints – set all Endpoint variables as impute only.
 1. Instead of clicking use tab and I, plus directional keys to change this.
 - d. Output tab
 - i. Tick imputation model, descriptive statistics and create iteration history – name ComA1_iter
 - e. Double check – click ok
3. Save the imputed and iterations files.

Sequence for multiple imputation.

BLNFS, BLDGendermale1female2, BLBMI, BLNEnergykcal, BLNCarbohydrateg, BLNProteing, BLNFatg, BLN Sugarsg, BLNFreeSugarsg, BLNFibreg, BLNSaturatedFatg, BLSSodiumNamg, BLWeightkg, BLWaistcircumferencecm, BLLTEShealthscore, BLFCQ1Health, BLFCQ2Mood, BLFCQ3Convenience, BLFCQ4SensoryAppeal, BLFCQ5NaturalContent, BLFC1Q6Price, BLFCQ7WeightControl, BLFCQ8Familiarity, BLFCQ19EthicalConcern, BLSQPC1Personalimpact, BLSQPC2Personalmanagement, BLSQPC3Nonchalance, BLSQPC4Negativity, BLSQPC5Perceivedunderstanding, BLSQPC6PerceivedNonautonomy, BLSF36PCS, BLSF36MCS, BLTSEQ CR, BLTSEQQUE, BLTSEQEE. *Followed by imputation only variables

Get pooled descriptives for analysis / comparison to my values.

1. Data - Split file
 - a. Click split file in ComA1_imp
 - b. Click compare groups
 - c. By imputation number_variable
 - d. Ok
2. Analyze – Descriptive statistics
 - a. Descriptives
 - b. Input all BL and EP variables apart from BL OG FS%.
 - c. Scroll to bottom of output table for pooled means – SD will be calculated from average of 20 imputations at a later date and are not shown here.

BLINDING

The main researcher had no knowledge of allocated groups of participants and was blinded during all data handling and imputation.

DATA ANALYSIS

Outcomes

Primary outcomes were % TEI from free sugars (%FS), and adherence to the recommendations at 12 weeks. Secondary outcomes were dietary profiles (daily energy intake, dietary composition, food consumption), anthropometry, sweet food perceptions and preferences, sweet food choice, attitudes to sweet foods, attitudes towards eating behaviour, motives for food choice, knowledge and lifestyle variables, quality of life and adverse events at week 12; change between baseline and week 12 in key outcomes (%FS, daily energy intake, sugar-sweetened and sweetener-sweetened food consumption, anthropometry), %FS, adherence, dietary profiles and barriers and facilitators towards intervention adherence and success/failure in achieving the recommendations (subset only) at weeks 1, 2, 4 and 8. Demographic variables, and sweet taste sensitivity, sweet liker status and PROP (bitter taste) status were also assessed at baseline, to aid in the interpretation of all outcomes, considering associations between these variables and sweet taste perceptions, liking and food intakes (Jayasinghe et al., 2017; Yeomans et al., 2009).

Three distinct analyses were pre-specified in advance: 1) Analyses of the population as a whole to investigate the effects of the three different types of dietary recommendation versus control; 2) Analyses of the effects of the dietary recommendations in different population subgroups, and 3) Investigation of the barriers and facilitators to success.

Data presentation

Data will be presented as mean \pm standard deviation in all cases, unless stated. Values will be considered significant at the $p<0.05$ level. Before completing analyses, data will be checked for normality. The data set is large, $N=242$, thus a normal distribution will be assumed. Where assumptions of homogeneity of variance are violated (Levene's test $p<0.05$), statistics will be taken from analyses conducted assuming non-equal variances. Bonferroni corrections for multiple testing will be applied to data where tests were not pre-specified in the study protocol. Where multiple regression analyses are used, all variables will be checked for multicollinearity using correlation cut-offs of <0.7 . Pearson correlation values will be used for all continuous variables, and Spearman correlations for categorical variables.

Participant characteristics

Details of study completion will be provided and a CONSORT diagram created detailing number randomized to each group, number completing the study in each group, drop out and number included in all analyses.

Characteristics will be given for the whole sample and for each trial group.

Analyses One: Quantitative Data

For analyses one, multiple regression analyses will be used. Analyses will be conducted for both primary outcomes, for key secondary outcomes - daily energy intake, sugar-sweetened food intake, LCS-sweetened food intake, body weight, waist circumference, and adverse events; and change (baseline - week 12) data for these outcomes; and for other secondary outcomes (dietary

composition, sweet food perceptions and preferences, sweet food choice, attitudes to sweet foods, attitudes towards eating behaviour, motives for food choice, knowledge and lifestyle variables, quality of life) if differences are found in the sample as a whole from baseline to week 12. This will reduce the number of exploratory tests undertaken. Differences from baseline to week 12 will be investigated by paired t-tests. Primary outcomes and outcomes associated with dietary composition will also be investigated in the same manner at weeks 1, 2, 4 and 8.

Primary models will include gender, age, control/intervention group, baseline %FS, baseline body weight (as randomization variables), and baseline variable of interest. In analyses for %FS, sugar-sweetened food intake, LCS-sweetened food intake, body weight and waist circumference, TEI at Week 12 and physical activity at Week 12 will also be included. Secondary models will also include any additional variable that correlates with each outcome when assessed independently. All variables measured will be considered as secondary variables. Effects for all continuous variables will be investigated using linear multiple regression. Effects for adherence will be investigated using logistic regression to predict adherent vs not adherent.

Analyses Two: Quantitative Data

For analyses two, analyses one will be repeated for demographic groups where significant associations for these variables were found in analyses one. Analyses will only be conducted if significant associations are reported. If no significant associations with demographic variables are found, these analyses will not be completed. These analyses are intended to demonstrate differing effects of the intervention/s in different population groups.

Analyses Three: Qualitative Data

Analyses three will investigate the qualitative data collected from a subset of participants using solo interviews. These interviews were scheduled for completion in a sample of 80 participants from different intervention groups and at different time points. These analyses will be undertaken using a thematic framework analysis. First, a random sample of interviews will be analysed inductively using thematic analysis to identify codes. These codes will be used to create a framework and the framework then applied to all interviews.

Framework analysis has been chosen as a suitable analytical method for evaluating the qualitative interview data gathered, due to an interest in individual experiences and seeks to identify the different factors (barriers or facilitators) that contributed to successful or unsuccessful dietary change (Braun & Clark, 2013). The practical methods for conducting framework analysis follow a methodology as outlined below.

Framework analysis (Braun & Clarke, 2006; 2013; Gale et al, 2013).

Phase 1 'Familiarizing yourself: Transcribing data (if necessary), reading and re-reading the data, noting down with your data: initial ideas'.

- Audio data is transcribed, using automated timestamps and a published notation system in NVIVO software.
- To ensure high quality audio and transcription practises, Poland's (2001) 'Strategies for Ensuring High-Quality Tape Recording' will be used.

- All transcription is completed orthographically to produce a verbatim account. Data will be re-read and checked to ensure accurate transcription. Once the researcher has completed the transcription, data will be anonymised, and the audio file destroyed.

Phase 2 'Generating initial codes: Coding interesting features of the data in a systematic fashion across the entire data set, collating data relevant to each code.'

- Using a process of complete coding, initial codes will be generated after the transcription of the first 12 interviews.
- The data set will only be considered saturated, once fewer than 5% of new codes are identified in on-going analyses. Two additional transcripts will be required at this point to confirm saturation.
- Once the data saturation is confirmed, inter-rater reliability will be tested.
 - Two randomly (computer generated number selection) selected transcripts and the coding book will be provided to a second coder for this test.
 - Only once substantial coding agreement between the researcher and second coder has been achieved ($\kappa = >0.61$)(80) can phase 3 begin.

Phase 3 'Developing a working analytical framework.'

- After reaching saturation as agreed above, the researchers will meet and agree the codes for all subsequent transcripts. These codes are then grouped together into categories or themes.

Phase 4 'Applying the analytical framework'

- All transcripts are to be coded according to the agreement in phase 3.
- All candidate themes will be reviewed and checked to ensure a coherent theme pattern is present.
- Then the whole data set will be reviewed providing answers to these questions.
 - Do the themes work in relation to the whole data set?
 - Does any re-coding of data within themes need to be completed?
 - Has anything been missed from the initial coding?

Phase 5 'Charting data into the framework matrix'

- Data from transcripts will be charted into an excel spreadsheet outlining each interview and the extracted quotes (and location reference) for each code.

Phase 6 'Interpreting the data'

- Characteristics and difference between groups and interview timepoints will be analysed.
- Mapping connections between relationships and categories.
- A 15-point check list from Braun & Clarke 2013 and consolidated criteria for reporting qualitative research (COREQ) will be used in the write-up and reporting of this qualitative research.

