7.3 PARTICIPANT TESTING

Baseline and end assessments will be conducted in a single session for all participants. Sessions will last approximately 30-60 min., and will be conducted at Bournemouth University where possible, or in the participant's home via Zoom. 'At-home' test sessions will be used if participants are unable or unwilling to come to the University, and are intended primarily to allow the trial to continue during the COVID-19 pandemic when National lockdown measures and precautions were recommended in the UK (March 2020 - July 2021). These home test sessions may also open the trial to participants who would otherwise be unable to take part, primarily due to location, enhancing study inclusivity. Participants will be tested in the same location at both baseline and trial end, as possible.

All participants will complete the same measures regardless of their completion of test sessions at the University or 'at-home', with a few exceptions: Participants who are tested 'at-home' will not undertake the sweet taste perception and preference tests, the sweet food choice test, nor the solution-based measures of sweet liker status. Participants who are tested 'at-home' will also complete their own anthropometric measurements, but they will do this while the trial researcher observes via Zoom. Comparability across all measurements will be facilitated by involvement of the same researcher both at the University or 'at-home'.

All sessions will commence before 11am to allow individuals to undertake the measures in a fasted state, and will begin at the same time at baseline and trial end. The day before testing participants will also be asked to consume no alcohol, to consume nothing after 10pm, and to undertake no heavy exercise. Measures will be undertaken in the same order during each test session, as follows, or simply omitted: anthropometry; saliva sample; sweet liker status; PROP taste test; sweet taste test; and sweet food choice test. All questionnaires will be completed and checked for completion before the test session.

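### The SAP does not limit imputation and analysis of the lab-only sweet taste and sweet food choice outcomes to people tested in the lab; run on the full dataset, its listed steps would shrink the arm contrasts

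*SAP*

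**What the plan says.** Protocol 7.3 lets the baseline and end sessions take place at the University or at home by video call. The home "test sessions will be used if participants are unable or unwilling to come to the University". People tested there "will not undertake the sweet taste perception and preference tests, the sweet food choice test, nor the solution-based measures of sweet liker status". Location is held constant only where feasible: "Participants will be tested in the same location at both baseline and trial end, as possible".

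Protocol section 6 and the SAP's Outcomes paragraph both name sweet food perceptions and preferences and sweet food choice as secondary outcomes. Protocol Table 2 schedules both tests at baseline and week 12.

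On missing values, the SAP section on multiple imputation says: "The same multiple imputation guidelines were used for the basis for the imputation of all missing data". It then says: "The same multiple imputation model was run for the initial analyses, adherence and variables completed by only lab participants". It adds a rule for incomplete variables: "Where variables presented as having missing data, they were set as 'impute only' to ensure all predictor variables were not based on imputed data".

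The SPSS steps that follow set 20 imputations and predictive mean matching from the 5 closest donors. They include no case selection. The printed predictor sequence runs from baseline free sugars, gender and BMI through baseline nutrients, anthropometry and questionnaires. Neither trial arm nor test location is in it.

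Under Analyses One, arm regressions on these outcomes are run only if a paired t-test shows a change from baseline to week 12 in the whole sample.

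**The concern.** A taste score absent because the person was tested at home differs from one lost to dropout. It was never going to be measured, and usually both the baseline and the week-12 value are absent. Imputing it adds no information about the effect of the recommendations. If at-home participants enter the run, each contributes a regression row whose baseline and outcome are both borrowed from lab donors.

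Two consequences would follow under the imputation model as listed. First, donors are chosen without regard to arm, so the imputed scores show no arm difference and pull the contrasts toward zero. Second, including at-home people makes the baseline taste scores incomplete. The impute-only rule would then bar those scores as predictors, even for lab participants who drop out later.

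At stake are the comparisons between arms on two named secondary outcomes.

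**Working it through.** **Plan's own figure.** There is none to reproduce. The documents give neither the number tested at home nor an N for the lab-only outcomes.

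**Inputs**
- Dropout d = 20%: the attrition allowance in Protocol 4.2.
- 60 per arm, four arms: Protocol 4.2.
- At-home share h: not given; assumed 10%, 30% and 50%.
- Imputation: 20 imputations, 5 donors, no arm among the predictors (SAP imputation steps and sequence).

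**Step 1, expected shrinkage.** Suppose home testing and dropout do not depend on arm. A fraction p of each arm then has an observed week-12 score and shows the true difference δ. The remaining 1 − p are filled from donors pooled over arms and show, on average, no difference. The expected estimate is p·δ + (1 − p)·0 = p·δ.

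- Everyone imputed: p = (1 − h)(1 − d)
  - h = 10%: 0.90 × 0.80 = 0.72
  - h = 30%: 0.70 × 0.80 = 0.56
  - h = 50%: 0.50 × 0.80 = 0.40
- Lab participants only, same predictors: p = 1 − d = 0.80 at any h

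The part due to imputing at-home people is therefore the factor 1 − h: 0.72/0.80 = 0.90, 0.56/0.80 = 0.70, 0.40/0.80 = 0.50.

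**Step 2, simulation.** Four arms of 60, 250 repetitions per setting, predictive mean matching with 5 donors, 20 imputations, pooling by Rubin's rules. The regression was on arm, baseline score and one covariate. Assumptions: true effect 0.8 SD in one arm (the standardised difference in Protocol 4.2, set there for free sugars and borrowed only to illustrate); baseline to week-12 correlation 0.5; covariate to baseline-score correlation 0.3. The baseline score was a predictor only in the lab-only runs, where it is complete.

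Share of the true effect kept (power), with 20% dropout:

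| Population and imputation model | h = 10% | h = 30% | h = 50% |
|---|---|---|---|
| Everyone, no arm (as listed) | 74% (0.87) | 56% (0.52) | 38% (0.10) |
| Lab only, no arm | 82% (0.96) | 80% (0.89) | 78% (0.72) |
| Everyone, arm added | 101% (0.96) | 99% (0.88) | 91% (0.63) |
| Lab only, arm added | 102% (0.98) | 99% (0.97) | 95% (0.85) |

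The first row agrees with Step 1 (72%, 56%, 40%) to within 2 percentage points. Without dropout at h = 30%, imputing everyone without arm keeps 69% (formula 70%) and the lab-only limit keeps 99%.

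**Step 3, what remains once arm is in the model.** At h = 30% with dropout, the average standard error is 0.250 when everyone is imputed and 0.211 for lab only. The ratio 0.250/0.211 is about 1.18. Adding arm removes the bias at h = 10% and 30%, but imputing at-home people still costs precision.

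**Step 4, is the lab subset a fair comparison?** Protocol 4.3 and 7.2 place allocation after the baseline measures. Baseline location is therefore settled before allocation, and a filter on it keeps a randomised comparison.

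**The case against.** The strongest objection is that no sentence says scores were created for people tested at home. The SAP names three imputation jobs, and the third may be a separate run within the lab group. Other SAP text fits that reading: all baseline variables are said to serve as predictors, only endpoint variables are set to impute-only in the steps, and one missing baseline waist value is given as the sole exception. With at-home people included, every baseline taste score would be a further exception. This stands. A reader might infer that at-home scores were certainly invented, and the documents do not support that. What they do show is a scope covering all missing values, listed steps with no case filter, and no stated population.

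A second objection is that the dilution belongs to the omission of arm. That is largely right, as the third row of the table shows. It does not dispose of the point. Under the predictors as listed, the lab-only limit alone raises the share kept at h = 30% from 56% to 80%, and with arm added it still narrows the intervals. Equally, the limit is not a full repair, because about 20% dilution from dropout remains until arm is included.

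Three further inferences should be resisted:
- The calendar might suggest h of about 3/18 = 17% (May to July 2021 within an 18-month trial). Protocol 7.1 expects uneven recruitment and 7.3 keeps home sessions open to others, so h may be lower or higher.
- The choice of 20 imputations might look too low for these variables. The SAP justifies that number for the main analyses only.
- The sentence "The data set is large, $N=242$, thus a normal distribution will be assumed" might be read as the N for the taste outcomes. It supports a normality assumption and does not state that N.

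Nor can it be said that someone tested at home never has these scores, since a participant may change location between sessions.

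**Conclusion.** The concern holds in a limited form. The SAP leaves undefined who is imputed and who is analysed for sweet taste perception and preference and for sweet food choice. Followed literally on the full dataset, its steps would fill in at-home scores without regard to arm. The contrasts would then keep about 72%, 56% or 40% of a true effect at h = 10%, 30% or 50%, against about 80% with the lab-only limit alone.

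These figures rest on an assumed h, 20% dropout, home testing and dropout unrelated to arm, and the printed predictor list carrying over to the lab-only run. The power figures rest also on the illustrative 0.8 SD effect. If the run was in fact confined to lab participants, the loss tied to h disappears and only the missing statement remains.

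The reach is narrow. The primary and key secondary outcomes are not affected, and the SAP runs arm models for these outcomes only after a whole-sample change. The correction should be made, but it does not threaten the trial's main conclusion.

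**What to change.** State in the SAP that, for sweet taste perceptions and preferences and for sweet food choice:
- the imputation and analysis population, including the paired test that precedes the regressions, is all randomised participants whose baseline session was at the University;
- these variables are not imputed for participants whose baseline session was at home;
- within the lab population, only week-12 values lost to dropout or to a missed or relocated session are imputed;
- the imputation model uses the complete baseline score of the outcome and masked trial arm as predictors;
- N is reported by arm for these outcomes.

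The cost is a few lines of SAP text, one filter on baseline location, and a rerun of this imputation with a coded arm variable, which keeps the analyst blinded. The results will generalise only to people tested in person. Anyone tested at home at baseline but in the lab at week 12 is left out of these analyses.
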